### 7.3 Management of specific toxicities related to everolimus

Overall, safety data available from completed, controlled and uncontrolled studies indicate that everolimus is generally well tolerated at weekly or daily dose schedules. The safety profile is characterized by manageable adverse events (AEs). These AEs are generally reversible and non-cumulative.

Adverse events most frequently observed with everolimus are stomatitis, rash, fatigue, diarrhea, infections, nausea, decreased appetite, anemia, dysgeusia, pneumonitis, edema, peripheral hyperglycemia, asthenia, pruritis, weight decrease, hypercholesterolemia, ,

epistaxis, cough and headache. Overall, the most frequently observed laboratory abnormalities include decreased hematologic parameters including hemoglobin, lymphocytes, platelets, and neutrophils (or collectively as pancytopenia); increased clinical chemistry parameters including cholesterol, triglycerides, glucose, aspartate transaminases, creatinine, alanine transaminases, and bilirubin; and decreased clinical chemistry parameters including phosphate and potassium. The majority of these AEs have been of mild to moderate severity (NCI CTC grade 1-2).

### **7.3.1 Management of infections**

Everolimus has immunosuppressive properties and may predispose patients to bacterial, fungal, viral or protozoal infections, including infections with opportunistic pathogens. Localized and systemic infections, including pneumonia, other bacterial infections, invasive fungal infections, such as aspergillosis or candidiasis and viral infections including reactivation of hepatitis B virus, have been described in patients taking Everolimus. Some of these infections have been severe (e.g. leading to respiratory or hepatic failure) and occasionally have had a fatal outcome.

Physicians and patients should be aware of the increased risk of infection with Everolimus. Treat pre-existing infections prior to starting treatment with Everolimus. While taking Everolimus, be vigilant for symptoms and signs of infection; if a diagnosis of infection is made, institute appropriate treatment promptly and consider interruption or discontinuation of Everolimus.

If a diagnosis of invasive systemic fungal infection is made, discontinue Everolimus and treat with appropriate antifungal therapy.

### **7.3.2 Management of skin toxicity**

For patients with grade 1 toxicity, no specific supportive care is usually needed or indicated. Rash must be reported as an AE. Patients with grade 2 or higher toxicity may be treated with the following suggested supportive measures at the discretion of the investigator: oral minocycline, topical tetracycline, topical clindamycin, topical silver sulfadiazine, diphenhydramine, oral prednisolone (short course), topical corticosteroids, or pimecrolimus.

### **7.3.3 Management of Hypersensitivity reactions**

Hypersensitivity reactions manifested by symptoms including, but not limited to, anaphylaxis, dyspnea, flushing, chest pain or angioedema (e.g. swelling of the airways or tongue, with or without respiratory impairment) have been observed with everolimus. Management of hypersensitivity reactions will be up to the treating co-investigator's discretion.

### 7.3.4 Renal Failure Events

Cases of renal failure (including acute renal failure), some with fatal outcome, occurred in patients treated with everolimus. Renal function of patients should be monitored particularly where patients have additional risk factors that may further impair renal function.

Elevations of serum creatinine, usually mild, and proteinuria have been reported in patients taking everolimus. Monitoring of renal function, including measurement of blood urea nitrogen (BUN), urinary protein, or serum creatinine, is recommended prior to the start of everolimus therapy and periodically thereafter.

### 7.3.5 Management of stomatitis / oral mucositis / mouth ulcers

Adverse Drug Reaction/severity	Afinitor Dose Adjustment and Management Recommendations	
Grade 1 Stomatitis Minimal symptoms, normal diet	No dose adjustment required. Manage with non-alcoholic or salt water (0.9%) mouth wash severaltimes a day.	
Grade 2 stomatitis Symptomatic but can eat and swallow modified diet	Temporary dose interruption until recovery to grade $\leq 1$ . Re-initiate Afinitor at same dose. If stomatitis recurs at grade 2, interrupt dose until recovery to grade $\leq 1$ . Re-initiate Afinitor at lower dose. Manage with topical analgesic mouth treatments (e.g. benzocaine, butyl aminobenzoate, tetracaine hydrochloride, methol or phenol) with or without topical corticosteroids (i.e. triamcinolone oral paste)*.	
Grade 3 stomatitis Symptomatic and unable to adequately eat or hydrate orally	Temporary dose interruption until recovery to grade $\leq 1$ . Re-initiate Afinitor at lower dose. Manage with topical analgesic mouth treatments (i.e. benzocaine, butyl aminobenzoate, tetracaine hydrochloride, methol or phenol) with or without topical corticosteroids (i.e. triamcinolone oral paste)*	
Grade 4 stomatitis Symptoms associated with life-threatening consequences	Grade 4 Discontinue Afinitor and treat with appropriate medical therapy.	

\* using agents containing hydrogen peroxide, iodine, and thyme derivatives in management of stomatitis as they may worsen mouth ulcers.

Patients with a clinical history of stomatitis/mucositis/mouth ulcers and those with gastrointestinal morbidity associated with mouth/dental infections, irritation of esophageal mucosa e.g. gastroesophageal reflux disease (GERD) and pre-existing stomatitis/mucositis must be monitored even more closely. Patients should be instructed to report the first onset of buccal mucosa irritation/reddening to their study physician immediately.

Stomatitis/oral mucositis/mouth ulcers due to Everolimus should be treated using local supportive care. Please note that investigators in earlier trials have described the oral toxicities associated with Everolimus as mouth ulcers, rather than mucositis or stomatitis. If your examination reveals mouth ulcers rather than a more general inflammation of the mouth, please classify the adverse event as such. The suggested paradigm for treatment of stomatitis/oral mucositis/mouth ulcers is as follows:

1. For mild toxicity (grade 1), no dose adjustment required. Manage with non-alcoholic mouth wash or salt water (0.9%) mouth wash several times a day until resolution.
2. For more severe toxicity (grade 2 in which case patients have pain but are able to maintain adequate oral alimentation, or grade 3 in which case patients cannot maintain adequate oral alimentation), the suggested treatments are topical analgesic mouth treatments (i.e., local anesthetics such as, benzocaine, butyl aminobenzoate, tetracaine hydrochloride, menthol, or phenol) with or without topical corticosteroids, such as triamcinolone oral paste 0.1% (Kenalog in Orabase®).
3. Agents containing alcohol, hydrogen peroxide, iodine, and thyme derivatives may tend to worsen mouth ulcers. These agents should be avoided.
4. Antifungal agents should be avoided unless a fungal infection is diagnosed. In particular, systemic imidazole antifungal agents (ketoconazole, fluconazole, itraconazole, etc.) should be avoided in all patients due to their strong inhibition of Everolimus metabolism, therefore leading to higher Everolimus exposures. Therefore, topical antifungal agents are preferred if an infection is diagnosed. Similarly, antiviral agents such as acyclovir should be avoided unless a viral infection is diagnosed.

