## **7.0 DOSE MODIFICATION**

NCI Common Terminology Criteria for Adverse Events. This study will utilize the CTCAE (NCI Common Terminology Criteria for Adverse Events) Version 4.0 for toxicity and Serious Adverse Event reporting. A copy of the CTCAE Version 4.0 can be downloaded from the CTEP home page (<http://ctep.cancer.gov>). The dose modifications are for events that are possibly, probably or definitely related to the study drug.

Missed doses are to be omitted rather than made up. If multiple toxicities are experienced, dose modifications will be based on the toxicity requiring the largest dose reduction. Reductions are based on the dose given in the preceding reporting period and

are based on toxicities observed since the prior toxicity evaluation. Once dose is reduced, patients will continue at new dose. No dose reescalations are allowed. There are no dose modifications for endocrine therapy.

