### Special Populations

Geriatrics ( $\geq 65$  years) :

No dosage adjustment is required.

Renal impairment :

No dosage adjustment is required.

Ethnicity :

Pharmacokinetic characteristics are similar for Caucasian and Japanese subjects.

Pharmacokinetic studies in Black transplant patients have shown an average 20% higher clearance.

**Table 2** Study treatment schedule adjustments and dose levels

Dose level	Dose and schedule
0 (starting dose)	10 mg/day
-1	5 mg/day
-2	2.5 mg/day

- If a patient is already at dose level -2 and again meets criteria for dose reduction, everolimus will be discontinued and the patient will continue on study treatment with the aromatase inhibitor therapy only.

Table 3 and Table 4 list the dosing guidelines for Everolimus-related non-hematologic and hematologic toxicities.

**Table 3** Dosing guidelines for Everolimus-related non-hematologic toxicities

Toxicity	Action
Non-Infectious Pneumonitis	Please refer to Table 0.
Reactivation of HBV or HCV flare	
Patients with a known diagnosis of hepatitis B or C infection will be excluded from study participation. Patient who meet criteria for hepatitis B or C screening and are found to have positive serology indicating an ongoing infection, will be excluded from study participation. For all other patient who start study treatment and are subsequently found to have a hepatitis B reactivation or hepatitis C flare, please refer to tables 6 and 7.
 
Table

AST or ALT elevation Grade 1 ( $>$ ULN - 3.0 x ULN) Grade 2 ( $>$ 3.0 - 5.0 x ULN)	Maintain current dose level
AST or ALT elevation Grade 3 ( $>$ 5.0 - 20.0 ULN)*	
Interrupt Everolimus administration until resolution to <math>\leq</math> grade 1 (or <math>\leq</math> grade 2 if baseline values were within the range of grade 2). If resolution occurs <math>\leq</math> 7 days, Everolimus should be re-started at the dose level prior to interruption.
 
If resolution takes <math>></math> 7 days, or if event recurs within 28 days, hold Everolimus until recovery to <math>\leq</math> grade 1 or baseline grade / value and reintroduce Everolimus at one dose level lower, if available.

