AST or ALT elevation Grade 4 ( $>$ 20 x ULN)*	
Interrupt Everolimus administration until resolution to <math>\leq</math> grade 1 (or <math>\leq</math> grade 2 if baseline values were within the range of grade 2). If resolution occurs <math>\leq</math> 7 days, Everolimus should be re-started at one dose level lower. If resolution takes <math>></math> 7 days, discontinue Everolimus.

Recurrence of grade 4 after dose reduction or toxicity requiring Everolimus interruption for $>$ 28 days	Discontinue Everolimus.
Intolerable grade 2 mucositis, or grade 3 AE, except hyperglycemia or hypertriglyceridemia or hypercholesterolemia (see Section 7.3.6 )	
Interrupt Everolimus administration until resolution to <math>\leq</math> grade 1 or baseline grade / value.
 
If resolution occurs within <math>\leq</math> 7 days, Everolimus should be re-started at the dose level prior to interruption.
 
If resolution takes <math>></math> 7 days, or if event recurs within 28 days, hold Everolimus until recovery to <math>\leq</math> grade 1 or baseline grade / value and reintroduce Everolimus at one dose level lower, if available.
 
Patients will be withdrawn from the study if they fail to recover to <math>\leq</math> grade 1 or baseline grade / value within 28 days.

Any other grade 4	Hold Everolimus until recovery to grade $\leq$ 1 or baseline value Reintroduce Everolimus at one dose level lower, if available.
Grade 3 or 4 clinical liver failure (asterixis or encephalopathy/coma)	Discontinue Everolimus
Recurrence of intolerable grade 2 mucositis or grade 3 event after dose reduction	Reduce dose to the next lower dose level, if available. The lowest possible dose level of Everolimus is 2.5 mg daily. Below this level, Everolimus must be discontinued.
Recurrence of grade 4 after dose reduction	Discontinue Everolimus

Toxicity	Action
Any non-hematologic toxicity requiring Everolimus interruption for > 28 days	Discontinue Everolimus

\* Should HCV flare be confirmed, the guidelines for flare must take precedence (Table )

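### Table 3 and section 7.3.5 set different everolimus restart doses in three stomatitis situations; no rule says which governs, and a reduced dose cannot be raised again

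*Combined protocol and SAP*

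**What the plan says.** **Table 3 (section 7.2).** One row is headed "Intolerable grade 2 mucositis, or grade 3 AE, except hyperglycemia or hypertriglyceridemia or hypercholesterolemia". Everolimus is held until recovery to grade 1 or below, or to baseline. If that takes 7 days or less, "Everolimus should be re-started at the dose level prior to interruption". The alternative branch applies when resolution takes more than "7 days, or if event recurs within 28 days, hold Everolimus until recovery to" grade 1 or baseline, and then reintroduces the drug one dose level lower.

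**Section 7.3.5.** The table there also requires recovery to grade 1 or below before restart, but puts no time condition on the dose. For a first grade 2 event: "Re-initiate Afinitor at same dose". For a further one: "If stomatitis recurs at grade 2, interrupt dose until recovery to grade" 1 or below, then restart lower. For grade 3: "Re-initiate Afinitor at lower dose. Manage with topical analgesic mouth treatments (i.e. benzocaine, butyl aminobenzoate, tetracaine hydrochloride", and so on.

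**Section 7.0.** "Once dose is reduced, patients will continue at new dose. No dose reescalations are allowed".

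**Pointers.** For pneumonitis Table 3 says "Please refer to Table 0", and it sends hepatitis reactivation or flare to Tables 6 and 7. For mucositis, which it names in two rows, it gives no pointer to section 7.3.5.

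**The concern.** Stomatitis heads the list of common everolimus reactions in section 6.1.1, which is given in decreasing order of frequency, so sites can expect to use these rules. The two texts rest on different criteria and can give different restart doses for one event. Because a reduction is permanent, the text a site happens to consult can fix the patient's maximum dose for the rest of the 26 weeks.

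What is at stake is patient safety and uniform treatment across the participating centers, in a trial whose first secondary objective is tolerability.

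**Working it through.** No figure in the plan bears on this point, so the check sets the two rules side by side.

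**Inputs**
- Dose levels (Table 2): 10, 5 and 2.5 mg/day.
- Table 3 rule: same dose if resolved in 7 days or less and not a recurrence within 28 days; otherwise one level lower.
- Section 7.3.5 rule: grade 3 lower; first grade 2 same; recurrent grade 2 lower.
- Population: patients with no earlier dose reduction. For grade 2, intolerable events only, since the Table 3 row covers no others.

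**Comparison** (each cell: Table 3 / section 7.3.5)

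| Event | Resolved in 7 days or less | Resolved in more than 7 days |
|---|---|---|
| Grade 2, first | same / same | **lower / same** (case 2) |
| Grade 2, recurs within 28 days | lower / lower | lower / lower |
| Grade 2, recurs after 28 days | **same / lower** (case 3) | lower / lower |
| Grade 3, first | **same / lower** (case 1) | lower / lower |
| Grade 3, recurs within 28 days | lower / lower | lower / lower |
| Grade 3, recurs after 28 days | **same / lower** (case 1) | lower / lower |

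Four of the 12 cells differ. The two grade 3 cells are one situation, which leaves three cases. The last row arises only if an earlier grade 3 episode was restarted without a reduction, that is, if the site had followed Table 3. The count describes the grid and says nothing about how often a site would meet a conflict.

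**Size per patient.** From the 10 mg/day starting dose, one level lower is 5 mg/day. So the choice is 10 or 5 mg/day.

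**Direction.** Section 7.3.5 is the stricter text in cases 1 and 3, and Table 3 in case 2. Always following one text is therefore not always the cautious choice.

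**Search for a precedence rule**
- Section 7.0 applies the largest reduction when a patient has several toxicities. Here there is one toxicity and two rules.
- The footnote to Table 3 gives precedence only to the hepatitis C flare guidelines.
- Table 3 is labelled as guidelines and the 7.3.5 table as recommendations. Neither label ranks them.
- Section 8.1.1 returns a dose to its earlier level only after an interacting drug is stopped. That does not concern reductions for toxicity.

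**The case against.** The best defense is that a specific rule displaces a general one. Section 7.3 deals with named toxicities, and for grade 3 the Table 3 row is generic, so a careful reader could follow 7.3.5 in case 1. That is reasonable for grade 3 but weaker for grade 2, where Table 3 names mucositis itself. Even for grade 3 it has to be inferred, although the same table writes out its pointers for pneumonitis and hepatitis.

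It is also fair to say that the conflict is conditional. The texts agree in most of the grid, and tolerable grade 2 events are outside the Table 3 row.

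Several stronger readings are tempting, and the documents do not support them:
- *That a patient with active grade 3 stomatitis is put back on 10 mg/day.* Both texts require recovery first, and Table 3 lowers the dose if the event recurs within 28 days.
- *That the loss of planned dose can be quantified by multiplying 5 mg/day by the remaining weeks.* Time of onset is not given. A 7-day hold cannot describe case 2. The sum also assumes no later hold or reduction in the patient restarted at 10 mg/day. It would be a ceiling, mainly for case 1, and not a general magnitude.
- *That the frequency class in section 6.1.1 bounds the number affected.* The class for grade 3/4 reactions (1/100 to under 1/10), applied to 33 patients, gives 33 × 0.01 = 0.33 to 33 × 0.10 = 3.3. But it comes from pooled data on related reactions, it is not split by time to resolution, 33 is an enrollment ceiling, and no rate is given for intolerable grade 2.
- *That grade 4 is a proven contradiction.* The Table 3 row for other grade 4 events restarts lower while 7.3.5 discontinues, but that row can be read as deferring to 7.3.5.
- *That patients who do not recover in 28 days are lost to the primary endpoint.* One Table 3 row withdraws them from the study and others only stop everolimus, but the study calendar note already asks for follow-up through surgery after stopping for toxicity.

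**Conclusion.** The inconsistency is real and should be corrected. For a patient with no earlier reduction, the two texts give different restart doses after recovery in three defined cases, 10 versus 5 mg/day from the starting dose. No stated rule chooses between them.

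This rests on three readings: the mucositis in Table 3 and the stomatitis in 7.3.5 are the same event, as the heading of 7.3.5 implies; the 28 days run from the earlier episode; and grade 3 stomatitis falls within the grade 3 row, whose only exceptions are metabolic.

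The number of patients affected cannot be derived. The sample size, the two-stage rule and the primary analysis are unchanged. Section 14.2 reports toxicity by worst grade and occurrence, so no planned summary depends directly on the restart dose. The matter is one of safety and uniform dosing.

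**What to change.** **Table 3**
- Add a row for stomatitis, mucositis and mouth ulcers that refers to section 7.3.5.
- Remove mucositis from the intolerable grade 2 / grade 3 row and from the recurrence row.
- Except stomatitis from the generic grade 3 and grade 4 rows.

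**Section 7.3.5.** The pointer alone would move case 2 to the less protective dose. To keep the stricter rule, add to the grade 2 row that if recovery takes more than 7 days, everolimus restarts one level lower. The small downside is a lower dose for those patients. That row does not separate tolerable from intolerable events, so the sponsor should say whether the added sentence covers both.

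**Minor clean-up.** The metabolic exception in Table 3 cites section 7.3.6, which is nausea; it should cite 7.3.8. The withdrawal and discontinuation wordings for non-recovery at 28 days should be reconciled. Whether the aromatase inhibitor then continues is a treatment decision for the sponsor.

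**Cost.** A protocol amendment to Table 3 and one sentence in 7.3.5, with the usual review and ethics approval. No new visits, procedures or patients.

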### **7.3.6 Management of nausea**

Routine premedication for nausea is not necessary, but symptomatic patients should be treated with standard antinausea/antiemetic therapy as necessary. If the patient vomits after taking the tablets, the dose should not be replaced. Patients should resume the next regularly scheduled dose.

### **7.3.7 Management of diarrhea**

Diarrhea has been reported with everolimus. In general, diarrhea has been transient, usually not of sufficient severity to hinder administration of study drug. Appearance of grade 1-2 diarrhea attributed to study drug toxicity may be treated with supportive care such as loperamide, initiated at the earliest onset (for example 4 mg orally followed by 2 mg orally every 2 hours until diarrhea-free for 12 hours).

### **7.3.8 Management of hyperlipidemia and hyperglycemia**

Dyslipidemia (including hypercholesterolemia and hypertriglyceridemia) has been reported in patients taking everolimus. Monitoring of blood cholesterol and triglycerides prior to the start of everolimus therapy and periodically thereafter as well as management with appropriate medical therapy is recommended.

Adverse Drug Reaction	Severity	Afinitor Dose Adjustment and Management Recommendations
Metabolic events (e.g. hyperglycemia, dyslipidemia)	Grade 1	No dose adjustment required. Initiate appropriate medical therapy and monitor.
	Grade 2	No dose adjustment required. Manage with appropriate medical therapy and monitor.
	Grade 3	Temporary dose interruption. Re-initiate Afinitor at lower dose. Manage with appropriate medical therapy and monitor.
	Grade 4	Discontinue Afinitor and treat with appropriate medical therapy.

Treatment of hyperlipidemia should take into account the pre-treatment status and dietary habits of the patient. Blood tests to monitor hyperlipidemia must be taken in the fasting state. Grade 2 or higher hypercholesterolemia ( $>300$  mg/dL or  $7.75$  mmol/L) or grade 2 hypertriglyceridemia or higher ( $> 300$  mg/dL -  $500$  mg/dL;  $>3.42$  mmol/L-  $5.7$  mmol/L) should be treated with a 3-hydroxy-3-methyl-glutaryl (HMG)-CoA reductase inhibitor (e.g. atorvastatin, pravastatin, fluvastatin) or appropriate triglyceride-lowering medication, in addition to diet.

Note: Concomitant therapy with fibrates and an HMG-CoA reductase inhibitor is associated with an increased risk of a rare but serious skeletal muscle toxicity manifested by rhabdomyolysis, markedly elevated creatine phosphokinase (CPK) levels and myoglobinuria, acute renal failure and sometimes death. The risk versus benefit of using this therapy should be determined for individual patients based on their risk of cardiovascular complications of hyperlipidemia.

Hyperglycemia has been reported inpatients taking everolimus. The fasting state of patients should be verified when interpreting results. Monitoring of fasting serum glucose is recommended prior to the start of everolimus and periodically thereafter. Optimal glycemic control should be achieved before starting a patient on Everolimus. More frequent monitoring is recommended when everolimus is co-administered with other drugs that may induce hyperglycemia.

